12.0 STATISTICAL METHODS

12.1 Analysis Principles

Enrolled subjects who provide product assessment data will be eligible for analysis; subjects who screen fail or did not provide any study product assessment data will be excluded from analysis.

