7.0 STUDY DESIGN

The study will be executed at a [REDACTED], and will not require [REDACTED]

[REDACTED] Subjects will be assigned to one of two possible study Groups. Group 1 will include subjects who currently use [REDACTED] IC products. Group 2 will include subjects who currently do not use [REDACTED] IC products but do use [REDACTED]. Subjects will be assigned either to Group 1 or Group 2 depending on their current hydrophilic IC product usage at time of completing the eligibility screener.

Subjects in Group 1 will be shipped [REDACTED] to use over a consecutive [REDACTED]. Subjects will be instructed to use Study Catheter [REDACTED] according to their usual care practices. After each day, subjects will complete a daily check-in to confirm the number of ICs they have remaining and if there have been changes in their overall health. Once the subject uses all of 30 study catheter [REDACTED] or [REDACTED] have elapsed, whichever occurs first, the subject will complete an end-of-study questionnaire about their overall experience.

Subjects in Group 2 will be shipped [REDACTED] IC [REDACTED]
[REDACTED] Subjects will first sample the currently marketed product for a [REDACTED], or until they use a maximum of 60 Study Catheter [REDACTED] whichever occurs first (“sampling period”). After the sampling period, subjects will switch to using Study Catheter [REDACTED] Subjects will use the study Catheter [REDACTED] for a consecutive [REDACTED], or until they have used all 30 Study Catheter [REDACTED] whichever occurs first. Subjects will be instructed to use both study catheters according to their usual care practices. After each day, subjects will complete a daily check-in to confirm the number of ICs they have remaining and if there have been changes in their overall health. After using both study catheters, the subjects in Group 2 will complete an end-of-study questionnaire about their overall experience.

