9.10 Subject Withdrawal

Subjects may elect to withdraw from the study at any time for any reason. Data collected up to the point of withdrawal will be eligible for analysis, unless the subject documents in writing to the PI that they refuse use of any and all of their data for analysis. Any new information gained during the study that might affect the subject's desire to continue participation will be conveyed to them in a timely manner. These

procedures are expressed in the ICF that the subject signs. Subjects electing to withdraw from the study are required to return all unused study product.

The Investigator may discontinue a subject from the study at any time without prejudice. Discontinuations are documented on [REDACTED] in the EDC system. Furthermore, the Sponsor may end the study at any time.

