11.0 DATA MANAGEMENT

It is the responsibility of the Investigator to ensure the completeness and accuracy of all study data collected in the EDC system. Subject name and contact information will be treated as Protected Health Information and not included in any dataset for analysis. All datasets for study analysis will include only de-identified data.

The electronic ICF and electronic case report forms (eCRFS) will be collected directly from research subjects using a secure, cloud-based EDC and electronic patient reported outcomes (ePRO) system [REDACTED]. [REDACTED] will be configured by the Sponsor Data Manager for study-specific data capture. Study forms such as the Adverse Event Form, Protocol Deviation Form, and Contact Log will be entered by the study personnel at the site.

Subjects will be provided with a link to the EDC/ePRO system via an email, as each study form is made available to them to complete. Subjects will set up their own, secure password to the system and that password remains unknown to the Sponsor. The [REDACTED] EDC will provide an audit log that verifies that all ePRO data were entered by the subjects themselves. The audit log will also document when and by whom any modifications were made to the data after initial entry.

To the best of the Sponsor's ability, data logic and validation checks will be configured in the ePRO system so that subjects will receive warning messages at time of entry regarding inconsistent or invalid entries, in order to assure quality and completeness of data. Because the study collects self-report data directly from the study participants, there will be minimal corrections or modifications by the Sponsor to ePRO data. Any modification of any ePRO data will only be done following direct contact and clarification from the research subject. There will be no modification to any data capturing subject opinion or assessment of study product. The Sponsor may contact the subject to clarify factual data, such as date of first study product use, or any unclear responses on the ICF and the Eligibility Screener, to assure proper and full consent of subjects, as well as confirmation of eligibility before study

enrollment. The Sponsor will contact any subject who directly reports or implies a change in their health status, in order to assure subject safety while using the study product.

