12.2 Incomplete Follow-up and Missing Data

In the event that a subject does not complete the full study period, the complete set of data available for that subject prior to loss-to-follow-up will be used for analysis. No imputation of missing data will be performed.

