13.2 Interim Analyses

An interim analysis is planned for when one of the following milestones occur, whichever occurs first: 1) [REDACTED] subjects have provided product assessment data via the end of study questionnaire or 2) the study reaches [REDACTED]. All subject data that has been gathered and released [REDACTED] on or prior to this milestone will be included in the interim analysis. [REDACTED]

[REDACTED] Any amendments will be documented per Section 17.0.

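### Section 12.1 makes product assessment data the condition for analysis with no visible limit to acceptability outcomes, so it is unsettled whether catheter users who stop before the end-of-study questionnaire count in AE summaries

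*Combined protocol and SAP*

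**What the plan says.** **Who is analysed.** Section 12.1 admits enrolled subjects who supply product assessment data and adds that "subjects who screen fail or did not provide any study product assessment data will be excluded from analysis". The sentence names no outcome to which it is confined, and the visible text does not define product assessment data.

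**Where such data come from.** Section 13.2 sets one interim milestone by how many "subjects have provided product assessment data via the end of study questionnaire". No other visible passage names a source. Section 9.7 lists one such questionnaire per subject. Section 7.0 places it at the end: in Group 1 when the 30 catheters are used or the period has run out, and in Group 2 after both catheters have been used.

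**Where safety data come from.** Section 5.1, under the primary objective, says that safety is monitored through the daily questionnaires. Section 7.0 describes these as a "daily check-in to confirm the number of ICs they have remaining and if there have been changes in their overall health". Section 11.0 says "Study forms such as the Adverse Event Form, Protocol Deviation Form, and Contact Log will be entered by the study personnel at the site". On subject opinion it has a separate rule: "There will be no modification to any data capturing subject opinion or assessment of study product".

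**Partial data.** For subjects who do not complete the study period, Section 12.2 says that "the complete set of data available for that subject prior to loss-to-follow-up will be used for analysis". Section 9.10 says "Data collected up to the point of withdrawal will be eligible for analysis", unless the subject refuses in writing. Section 10.1 adds that a subject who, in the Investigator's judgement, should no longer remain on the product is discontinued from the study.

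**The concern.** A condition suited to acceptability outcomes is worded as a condition for analysis in general. A subject with no opinion data cannot contribute to an acceptability percentage, so the exclusion is sensible there. It is not sensible for AEs, which come through other forms and can occur in anyone who used a catheter.

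The subjects at risk of omission are those who used a catheter and left early. Some may have left because of an AE, since Section 10.1 links coming off the product to leaving the study. If 12.1 is applied as worded, their AEs stay in the database but are missing from the summary table, and the subjects are missing from its denominator. Two competent analysts could therefore report different AE figures from the same data and each cite the protocol. What is at stake is the aggregate AE count and rate in any interim or final report, not the safety of individual subjects.

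**Working it through.** The plan gives no figure to reproduce: the sample size, margin of error and dropout rate in Section 12.4 are redacted, and no AE rate is stated. The main check is therefore a reading of the text.

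**Step 1: do daily health data satisfy 12.1?** Not clearly. Section 5.1 speaks of assessment data in connection with acceptability and mentions safety monitoring as an addition. Section 11.0 has AE forms entered by staff and treats subject opinion separately. Section 13.2 ties product assessment data to the end-of-study questionnaire. Nothing visible says that a catheter count or a reported health change counts as assessment.

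**Step 2: follow one subject.** An enrolled subject uses several catheters, reports a health change, has an AE Form completed, is discontinued under 10.1 and never completes the questionnaire.

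| Section | Result for this subject's AE |
|---|---|
| 10.1, 10.2 | Recorded and followed; reported where the criteria are met |
| 12.1, read literally | Subject is outside the analysis |
| 12.2, if the subject is lost to follow-up | Earlier data are used |
| 9.10, if the subject withdraws | Earlier data are eligible |

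Sections 12.2 and 9.10 can be read as keeping such a subject, or as acting only on subjects who have already met 12.1. No visible sentence gives precedence.

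**Step 3: what the two readings could do to an AE rate.** All inputs here are assumptions:
- q = share of catheter users with no questionnaire (taken to have no assessment data);
- pc = AE risk in users with a questionnaire;
- r = recorded-AE risk without a questionnaire divided by the risk with one.

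Rate in the 12.1 set = pc. Rate in all users = pc(1 − q) + r·pc·q. Gap = all-user rate minus 12.1 rate = q·pc·(r − 1). Share of AE subjects omitted = rq / (1 − q + rq).

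Example with pc = 10%, q = 10%, r = 2: gap = 0.10 × 0.10 × 1 = 0.01, or 1 point; share omitted = 0.20 / 1.10 = 18%. Per 100 users, the 12.1 set shows 9 of 90 (10.0%), while all users show 9 + 2 = 11 of 100 (11.0%).

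Gap in percentage points (share of AE subjects omitted), pc = 10%:

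| r | q = 5% | q = 10% | q = 20% |
|---|---|---|---|
| 0.5 | −0.25 (3%) | −0.5 (5%) | −1 (11%) |
| 1 | 0 (5%) | 0 (10%) | 0 (20%) |
| 2 | 0.5 (10%) | 1 (18%) | 2 (33%) |
| 3 | 1 (14%) | 2 (25%) | 4 (43%) |

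A positive gap means that the 12.1 rate is too low. With pc = 5% the gaps halve and the omitted shares do not change. Values of r above 1 are plausible if AEs lead to stopping. Values below 1 are plausible because early stoppers have less exposure and fewer daily forms.

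**The case against.** Several points on the other side have force.

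- **Redaction.** Section 13.1 breaks off into blacked-out text just after the generic descriptive methods. Section 10.3 and part of 13.2 are also blacked out, and the forms and the 9.7 event summaries are not shown. A reader might infer that the plan has no safety population. The documents do not support that: one may be defined in text that cannot be seen. This stands, and limits the point to the visible wording of 12.1.
- **Any assessment data may be a low bar.** Section 13.2 uses the questionnaire to set a milestone, not to define the term. If an unseen daily item counts as assessment, most early stoppers already satisfy 12.1. This stands as a possibility.
- **The sections can be reconciled.** If 12.1 removes everyone lost before the single questionnaire, 12.2 has little left to act on. The reading that gives 12.2 and 9.10 effect keeps these subjects. It is a reasonable reading, but the text does not state it.
- **Few subjects may be affected.** In Group 1 the questionnaire also falls due when the period elapses, so stopping use need not prevent completion, and nothing visible denies it to a discontinued subject. The share without a questionnaire could be near zero.
- **No AE rate is promised.** Section 15.0 does not describe the safety content of the reports, and no AE hypothesis or threshold is visible.

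A reader might also infer that AEs would go unrecorded, or that the reported rate would be too low. Neither follows. Section 10 capture does not depend on 12.1, and the gap can be positive, zero or negative.

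What the objections do not remove is that an unqualified exclusion, taken at its word, can drop a user with a recorded AE from an AE summary.

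**Conclusion.** The point holds as a defect in a stated rule, and it should be fixed before any AE summary is produced. Section 12.1 excludes from analysis without visible restriction, its key term is undefined, and its relation to 12.2 and 9.10 is not stated. The effect is confined to aggregate AE counts, rates and denominators.

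Its size and direction cannot be determined from the documents. Over the assumed grid above, the rate moves by −1 to +4 points at a 10% risk among those with a questionnaire, and 3% to 43% of subjects with an AE are omitted. These figures only show what could happen. They rest on the literal reading of 12.1, on the questionnaire being the only source of assessment data, and on redacted text not already providing a safety set. If either of the last two fails, the problem shrinks or disappears. Confidence is therefore medium.

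**What to change.** 1. In Section 12.1, limit the exclusion to product-acceptability outcomes and say what counts as product assessment data.
2. Summarise AEs in all enrolled subjects who used at least one study catheter, with or without a questionnaire, except those who refuse data use in writing under Section 9.10.
3. State in Sections 12.2 and 9.10 that they apply to that set.
4. If redacted text already defines such a set, cross-reference it in 12.1 instead.

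Catheter use can be established from data that the plan already describes: catheters remaining on the daily form (Section 7.0), date of first use (Section 11.0) and returned-catheter counts (Section 6.3).

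The cost is a few lines of text plus an amendment under Section 17.0, with review by the PI and IRB approval. Safety and acceptability denominators will differ and must be labelled, and the reported AE figure may move either way.

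Optional: show Group 2 AEs by period. Section 7.0 says "Subjects will first sample the currently marketed product", so a subject who stops during sampling has not used the modified catheter. This is a separate reporting choice that the 12.1 problem does not require. It depends on AE onset dates being recorded; for the AE Form, the visible text of Section 10.1 mentions only the date of resolution.

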5.0 STUDY OBJECTIVES

5.1 Primary Objective

The primary objective of this study is to assess [REDACTED] hydrophilic [REDACTED] technology used on the study product. Assessment data will be collected to determine whether end users find the [REDACTED] hydrophilic [REDACTED] technology to be [REDACTED] acceptable [REDACTED]
[REDACTED]
[REDACTED] Product safety will also be monitored through daily questionnaires intended to track adverse events.

[figure not shown]

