8.6 Subject Compensation

Subjects [REDACTED] will be offered [REDACTED] for their participation in the study. Compensation will be paid out by the Sponsor [REDACTED] subject completing the study procedures.

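### Users who leave while on the evaluated catheter may be missing from the acceptability result: 12.1 drops anyone unassessed, and the visible text names no assessment at exit

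*Combined protocol and SAP*

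**What the plan says.** All references are to the combined protocol and SAP. The evaluated catheter here means the modified study catheter that both groups use for up to 30 catheterizations.

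- **Objective (5.1).** "Assessment data will be collected to determine whether end users find the" technology acceptable (partly redacted). On safety: "Product safety will also be monitored through daily questionnaires intended to track adverse events".
- **Analysis set (12.1).** Enrolled subjects with product assessment data are eligible; "subjects who screen fail or did not provide any study product assessment data will be excluded from analysis".
- **Missing data (12.2, 9.10).** Data given before loss or withdrawal are used. Nothing is imputed.
- **Group 1 assessment (7.0).** When all 30 catheters are used or the period has elapsed, "whichever occurs first, the subject will complete an end-of-study questionnaire about their overall experience".
- **Group 2 assessment (7.0).** A sampling period on the marketed catheter comes first. The evaluated catheter is then used for a set period "or until they have used all 30 Study Catheter", whichever comes first. "After using both study catheters, the subjects in Group 2 will complete an end-of-study questionnaire about their overall experience".
- **Daily form (7.0).** It is described as "a daily check-in to confirm the number of ICs they have remaining and if there have been changes in their overall health".
- **Event list (9.7).** Both groups have consent, screener, baseline form, daily questionnaires and a single end-of-study questionnaire.
- **Exit (9.10, 10.1).** Withdrawing subjects must return unused product, and discontinuations are recorded on a form whose name is redacted. Neither section mentions an assessment.
- **Interim milestone (13.2).** It counts subjects whose product assessment data came through the end-of-study questionnaire, without saying that this is the only source.

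**The concern.** Giving up the evaluated catheter because of the catheter is itself evidence about acceptability. On the visible text, a user who does so and also leaves the study has no rating, so 12.1 removes that user from the result answering the primary question. The percentage then describes those who stayed, while 5.1 asks about end users.

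The group at issue is narrow: users of the evaluated catheter, in either group, who withdraw, are discontinued or stop responding before the questionnaire. Their exits are not lost to the study, because 10.1 has the investigator judge relatedness of adverse events and 9.10 documents discontinuations. What the visible text lacks is a link from those records to the acceptability result. The dropout allowance in 12.4 restores the number analysed, but not the opinions of those who left.

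**Working it through.** **No figure of the plan can be reproduced.** Sample size, margin of error and dropout rate are redacted in 12.4, and the acceptability criterion is not visible. Every number below is an assumption and shows possible size, not likely size.

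**Step 1. Who can be unassessed.** The evaluation ends in both groups when the period has elapsed or all 30 catheters are used. A dissatisfied user who stays enrolled therefore reaches the questionnaire. Only those who leave or fall silent first are affected.

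**Step 2. Bounds.** Let p be acceptability among those analysed and d the share of evaluated-catheter users without an assessment.

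- Lower bound (no unassessed user accepts): p(1 − d)
- Upper bound (all of them accept): p(1 − d) + d
- Width: d, whatever p is

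| d | p = 90% | p = 80% |
|---|---|---|
| 5% | 85.5% to 90.5% | 76.0% to 81.0% |
| 10% | 81.0% to 91.0% | 72.0% to 82.0% |
| 15% | 76.5% to 91.5% | 68.0% to 83.0% |
| 20% | 72.0% to 92.0% | 64.0% to 84.0% |

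If the measure is a mean (assumed 1 to 5 scale, 4.5 among those analysed, d = 10%), the lower bound is 4.5 × 0.9 + 1 × 0.1 = 4.15 and the upper is 4.5 × 0.9 + 5 × 0.1 = 4.55.

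**Step 3. Direction.** The overstatement is d × (p − q), where q is acceptability among the unassessed. With p = 90% and d = 10%:

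- q = 0%: 0.10 × 90 = 9.0 points
- q = 50%: 0.10 × 40 = 4.0 points
- q = 90%: 0
- q = 100%: 0.10 × (−10) = −1.0 point, a slight understatement

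For scale, the 95% margin of error 1.96 × √(0.9 × 0.1 / n) is 5.9 points at an assumed n = 100 and 8.3 at n = 50. Enrolling more subjects narrows that margin but does not reduce the shift.

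**Step 4. What exit forms would add.** Assume 100 users, 10 of whom leave, and 81 of the other 90 accept.

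- No exit forms: 81/90 = 90.0%; bounds 81/100 = 81.0% and 91/100 = 91.0%.
- Six leavers answer and 2 accept: 83/96 = 86.5% with exit ratings; bounds 83.0% and 87.0%.
- Six leavers answer and 5 accept: 86/96 = 89.6% with exit ratings; bounds 86.0% and 90.0%.

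The movement in the point estimate depends wholly on the assumed answers. The narrowing from 10 to 4 points depends only on how many leavers answer.

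**The case against.** The strongest reply is that the premise rests on what cannot be seen. The event summaries in 9.7, the attachments, the discontinuation form and part of 13.1 are missing or redacted in the public copy. A reader might infer that the plan has no exit assessment; the documents do not support that, and this point does not assert it.

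Nor is the end-of-study questionnaire shown to be the sole source of assessment data. 12.1 excludes only those with no such data at all, 9.10 and 12.2 preserve earlier data, and 13.2 may name one source among several. The daily form's purpose is described, but not its items. This stands as a limit. It does not close the gap, however: if an earlier form did count, the leaver would enter the analysis set still without an end-of-study answer, and 12.2 would leave that blank.

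Other parts of the reply also stand:

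- Use is capped at 30 catheters, and compensation appears tied to the "subject completing the study procedures" (8.6, partly redacted), so d may be small.
- An openly stated available-data analysis is a legitimate choice in an open-label, descriptive user-feedback study.
- Exit ratings may rest on very few catheters, so placing them in the main result is debatable.
- Exit forms are unlikely to reach users who have stopped responding. The count and bounds still cover those users.

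**Conclusion.** The point holds in a conditional form. On the visible text, evaluated-catheter users who leave early can drop out of the acceptability result, which would be too favourable if they left because of the product and little changed if they left for other reasons. The possible range equals the unassessed share d, for example 10 points at an assumed 10%. The actual share is unknown.

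Three stronger readings should be resisted:

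- **That the result will be biased upward.** Direction depends on why people leave, which the documents do not say.
- **That dissatisfied users in general are excluded.** Those who stay enrolled are assessed in both groups.
- **That Group 2 exits during the sampling period add to the problem.** Those subjects have not yet used the evaluated catheter.

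This is a low-cost improvement worth making, held with medium confidence because of the redactions.

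**What to change.** **1. Reporting (12.1, 12.2, 13.1).** Report, by group and reason, how many subjects used at least one evaluated catheter but have no assessment, drawing on the existing adverse event and discontinuation records. Show Group 2 sampling-period exits on a separate line. Beside the main result, give the lower and upper bounds over all evaluated-catheter users (for a mean, using the lowest and highest scale values). State in 12.2 that the bounds are sensitivity only and an explicit exception to the no-imputation rule. No unrated subject receives a rating in the main result.

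**2. Collection (9.7, 9.10).** Offer the existing end-of-study ePRO questionnaire at exit, voluntarily, to subjects who used at least one evaluated catheter. If an unseen form or event summary already does this, cross-reference it instead. Decisions to discontinue stay as they are. Show results with and without exit ratings, together with the number of catheters used by those who answered at exit. Exit ratings need not enter the main result, but the plan should say in advance whether they do.

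**Cost.** A small protocol and ICF amendment with IRB approval before use (17.0; 9.10 says the withdrawal procedures are in the ICF), one ePRO trigger for an existing form (11.0 already emails a link for each form), and one extra table. If an exit assessment already exists, part 2 needs only the cross-reference and the reporting statement. The sensitivity figures may look less favourable than the main result.
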